19.4.2. EFFICACY DATA

The primary analysis will be performed on the mITT population. Analyses conducted using the PP will be considered supportive.

CCI [REDACTED]
 CCI [REDACTED] will be calculated as the time in days from the date of the first dose of IMP. CCI [REDACTED]
 A log-rank sum test will be used to compare the treatment groups. Subjects completing the trial without CCI [REDACTED] or who are discontinued prematurely CCI [REDACTED], will be considered as censored at the time of their last follow-up.

CCI [REDACTED]
 CCI [REDACTED] will also be presented by treatment group. An appropriate non-parametric test will be used that makes allowing for the effect of prognostic covariates possible. This will be finalised in the SAP.

CCI [REDACTED]
 The number and the percentage of subjects CCI [REDACTED]

CCI [REDACTED]
 The CCI [REDACTED] total score and domain scores CCI [REDACTED] will be summarised at each visit by treatment group using descriptive statistics. Changes from baseline (Visit 2) will also be summarised for each post-baseline visit by treatment group. Scores will be computed according to the CCI [REDACTED] manual [18]. Multiple entries and missing data will be dealt with as described in the same manual.

CCI [REDACTED] will be analysed using a linear mixed model for repeated measures including treatment, visit, treatment-by-visit interaction, use of stable concomitant therapy with oral macrolides and pooled sites as fixed effects and baseline value as covariate. An unstructured covariance matrix will be assumed and the Kenward-Roger adjustment will be used for the degrees of freedom. The least square means in each treatment group, the least square mean differences between treatments, their 95% CIs and associated p-values at each visit will be estimated by the model.

The CCI [REDACTED] will be summarised and analysed similarly to the CCI [REDACTED]. Algorithm of scoring and methods for handling with multiple imputations and missing data will be performed according to the questionnaire instructions [20, 19].

CCI [REDACTED]
 The CCI [REDACTED] as determined by the mean change in CCI [REDACTED] from baseline (Visit 2) to Day 28 (Visit 3), as well as to Visits 5 and 7, will be compared between the treatment groups by an analysis of covariance model including treatment, pooled site and use of stable concomitant therapy with oral macrolides as fixed effects and baseline value as covariate. Least square means in each treatment group, least square mean difference between treatments, their 95% CIs and associated p-values will be estimated.

CCI [REDACTED] analyses may be conducted to assess the robustness of conclusions.

Summary statistics of the CCI and change from baseline (Visit 2) will be provided by treatment group for each trial visit.

CCI

Absolute and relative frequency of subjects CCI for CCI will be presented by treatment group along with the summaries for the CCI. Total number of CCI due to CCI per follow-up month will be collected during the study and described by treatment group.

19.4.3. SAFETY DATA

All safety endpoints will be summarised and analysed using the Safety Population.

Incidence of Treatment Emergent Adverse Events

The number and the percentage of subjects reporting TEAEs, treatment emergent SAEs, severe TEAEs, TEAEs leading to discontinuation and TEAEs leading to death will be presented by treatment group, along with the number of events occurring.

TEAEs will also be summarised by System Organ Class and Preferred Term according to MedDRA; they will additionally be summarised by severity and relationship to treatment. A separate summary table will be provided for SAEs.

Only TEAEs, i.e. events with an onset date on or after the date of IMP start, will be included in the summary tables. Individual data listings will include all AEs recorded; a separate listing will be provided for treatment-emergent SAEs.

Number of Subjects experiencing Bronchospasm Clinically or Spirometrically Determined following IMP Administration

The number of subjects experiencing bronchospasm spirometrically determined (a >15% decrease in FEV₁ – not due to poor technique - from pre-bronchodilator baseline in the 30 minutes post-IMP), or clinically determined, will be summarised by treatment. Percentages of subjects in each treatment group and the relative risk for colistimethate sodium group/placebo group will be provided with 95% CI. Treatment differences will be assessed using a Fisher Exact test.

The number and the percentage of subjects experiencing a bronchospasm following IMP administration as clinically determined will also be reported.

In addition, the results for FEV₁ and FVC at each visit will be summarised by treatment. Descriptive statistics for absolute and percentage changes from baseline, i.e. Visit 2 (pre-dose measurement) will be reported.

CCI

The number and percentage of subjects whose CCI at the end of treatment (at 12 months [Visit 7]) will be presented by treatment, overall and by status of previous usage of colistimethate sodium/colistin.

Vital Signs

Descriptive statistics for vital signs at Visit 1 and Visit 7 will be presented overall and by treatment.

Physical examination data.

Descriptive statistics for physical examination data at Visit 1 and Visit 7 will be presented overall and by treatment.

Haematology, clinical chemistry and renal function tests

Haematology, clinical chemistry and renal function test results at Visit 1, Visit 5, and Visit 7 will be converted to standard international units and summarised by treatment group using descriptive statistics for continuous variables. Summaries for change from Visit 1 at Visit 5, and Visit 7 will also be provided. Renal function tests will also be summarised at Visit 3. Frequency of subjects with values appearing outside the central laboratory normal range will be reported by visit for each treatment group. All values appearing outside the laboratory normal range will be highlighted in listings.

12-lead Electrocardiogram

Descriptive statistics for ECG results will be presented overall and by treatment.

Adherence and Exposure

Subject adherence will be analysed based on the data collected by the **CCI** logging system.

Adherence will be summarised by treatment group presenting descriptive statistics and percentages of adherent subjects, i.e. with at least 80% adherence.

The total number of doses of IMP taken by each subject, as recorded as part of the **CCI** logging system will be summarised as well.

19.4.4. HANDLING OF MISSING DATA

Generally, there will be no imputation of missing values and only observed data will be included in the analyses.

If an AE has a partial or fully missing date, and it is unclear whether the AE is treatment-emergent, it will be assumed that it is. In the AEs analysis, when relationship to study drug is missing for a TEAE it will be imputed to be drug-related.

Additional details of handling of missing data for each type of analyses will be provided in the SAP.

20. INFORMED CONSENT

Written informed consent will be obtained by the Investigator or other authorised person from all subjects or their legally acceptable representative.

The Investigator is responsible for correctly obtaining the informed consent in accordance with the applicable regulatory requirement(s), GCP and the ethical principles that have their origin in the Declaration of Helsinki.

Prior to the beginning of the trial, the Investigator must have received the EC/IRB written approval of the ICF.

Informed consent must be obtained prior to the initiation of any procedures specific to the trial. The record of the informed consent must be available to be audited/inspected by the Sponsor/CRO designees and by EC/IRB/CA(s), whenever requested.

The informed consent documentation must be personally dated and signed by the trial subjects, to confirm that consent is based on information that has been understood, and by the Investigator. The signature can also be from a legally acceptable representative (if applicable) in accordance with local law.

Neither the Investigator, nor the trial staff, should coerce or unduly influence a subject to participate or to continue to participate in a trial.

Before informed consent may be obtained, the Investigator or other authorised person, should provide the subject ample time and opportunity to inquire about details of the trial and to decide whether or not to participate in the trial. All questions about the trial should be answered to the satisfaction of the subject.

The subject should receive a copy of the signed and dated ICF and any other written information provided to him/her, and updates.

According to Directive 2001/20/EC, if the subject is not able to write, a verbal consent can be obtained. At least 1 impartial witness must be present during the obtaining of verbal informed consent.

Further, in case the subject and his/her legal representative are unable to read, informed consent will be obtained in the presence of an impartial witness, i.e. a person independent of the trial who will read the ICF and the written information to the subject.

21. ETHICS COMMITTEE/INVESTIGATIONAL REVIEW BOARD APPROVAL

This trial will be undertaken only after written and dated approval from an appropriate EC/IRB has been received by the Investigator and by the Sponsor for the CTP, all its appendices, ICF, and subjects' recruitment procedures (i.e. advertisements), if applicable.

In addition to the documents mentioned above, the EC/IRB will be provided with an updated SmPC and Investigator's Brochure, the Investigator's up-to-date Curriculum Vitae and/or other documentation evidencing qualifications, and any other documents that the EC/IRB may need to fulfil its responsibilities.

During the trial, on regular basis, the Investigator will have to submit written summaries of the trial status (i.e. recruitment rate) to the EC/IRB, if requested.

22. REGULATORY REQUIREMENTS

The trial is to be conducted in compliance with Federal regulations and the European legislations (Directive 2001/20/EC and Directive 2005/28/EC), the European Regulation 536/2014 and any applicable local regulations.

Selection of subjects will not start prior to the approval of the EC/IRB has been obtained and the trial notified to or authorised by CAs.

23. QUALITY ASSURANCE

This CTP has been audited by the Sponsor's Quality Assurance department. The Audit Plan for the study includes site audits and TMF audit. Audits will be planned and conducted according to the Sponsor's SOPs, whenever possible, depending on any travel restrictions due to Covid-19 and the impact of Covid-19 on clinical site activities.

24. INSURANCE

The Sponsor is concerned with the safety of the subjects in the clinical trial and wishes to protect the Investigator (and, as applicable per local regulations, the site, the monitor and all the Investigator's staff involved in the trial) in the event of claims or lawsuits alleging injury as a result of administration of a study drug.

In consideration of undertaking a human trial in subjects according to this CTP the Sponsor will:

- indemnify the Investigator and hold him without liability for claims for damages arising out of the above described investigation in excess to those covered by his/her own professional liability insurance;
- defend the Investigator against any claims or lawsuits initiated by, or on behalf of, subjects who seek damages for bodily injury alleged to have been sustained as a result of administration of the study drug;
- pay any settlements of judgement resulting therefrom, providing that for all of the aforementioned cases, the study drug was administered under the Investigator's supervision and in strict accordance with accepted medical practice, the CTP, and the precautions, indications, and other instructions, provided by the Sponsor;

Indemnification is not valid for claims for damages arising from malpractice and/or negligence on the part of the Investigator or those under the Investigator's supervision.

The protection afforded by this policy does not take the place of the Investigator's professional liability insurance, but covers damages in excess of such insurance protection. Additionally, this indemnity is conditional upon the Investigator giving the Sponsor information as soon as reasonably practicable and upon the Investigator assisting the Sponsor and its authorised representatives in the investigation and defence of any suit for which coverage is provided.

25. CLINICAL TRIAL REPORT

A CTR of the trial will be prepared and written by the CRO according to ICH topic E3 (CPMP/ICH/137/95). A summary of the report will be sent to Investigators/EC/IRB/Regulatory Authorities according to current regulations.

26. USE OF INFORMATION AND PUBLICATION

The Investigator agrees to inform Zambon in advance about his/her intention to divulge any data, results concerning the Confidential Information and/or the trial subject to this agreement. As a consequence hereof, Investigator hereby undertakes to submit to Zambon, at least with a 60 days (30 days in case of abstracts) prior written notice, the text and/or the content of the concerned publication, sufficient to allow Zambon to properly assess that such proposed publication respects and/or is not in conflict with Zambon's

rights to preserve and protect its intellectual property rights and any confidentiality imposed to Zambon by the prevailing rules of the country where the trial is conducted.

Further, without any prejudice to Investigator's right to divulge and save information for purposes stated herein-above, Investigator intends to seek Zambon opinion and advice on and prior to the intended publication and/or disclosure, in consideration also of the contractual relationship in force between Zambon and Investigator and the nature of the trial hereto.

28. APPENDICES

Appendix 1: Trial Flow Chart

Appendix 2: Investigator Signature Page

Appendix 1: Trial Flow Chart

VISITS	Visit 1 Screening	Visit 2 Randomisation	Phone call	Visit 3	Visit 4-6	Visit 7 EoT	Follow-Up 'Phone Call	Exacer- bation Visit
ACTIVITIES (see Sections 9 & 10 for details)	Within 45 Days of Visit 2*	Day 0	Day 7	Day 28 ± 1 week	Every 3 months ± 1 week	12 months ± 1 week	2 weeks ± 3 days after EoT	-----
Informed consent	X							
Medical history/demography	X							
Pregnancy test	X	X		X	X	X		
Vital signs	X					X		X
Physical examination	X					X		X
Previous/concomitant medications	X	X		X	X	X	X	X
12-lead ECG	X					X		
Obtain blood samples: Haematology and clinical chemistry/Renal Function/PK	X	X ^c		X ^{a, c}	X ^b	X		
Collect CCI sample	X	X		X	X ^d	X		X
Verify eligibility for randomisation	X	X						
Spirometry: FEV ₁ and FVC	X	X ^e		X	X	X ^e		X
CCI		X		X ^f	X	X		
CCI Training, Dispensing/Collection		X				X		
Review of IMP administration & CCI use (adherence)		X	X	X	X	X		
Study Medication: Dispense/Accountability		X		X	X	X		
Record of CCI and CCI			X	X	X	X		X
AE monitoring including exacerbations not otherwise reported	X	X	X	X	X	X	X	X
Weekly follow up phone calls to determine end of Pulmonary Exacerbations								X

* Informed consent must be obtained prior to any study procedure. Study procedures at Visit 1 can be performed any time prior to Visit 2.

^a; renal function test only. ^b; haematology, clinical chemistry and renal function test at Visit 5 (6 Months) only. ^c; PK sampling only (for relevant sites). ^d; Visit 5 only. ^e; FEV₁ and FVC to be measured pre-bronchodilator and 30 ± 10 minutes post IMP dose. ^f; The 4 week version of the **CCI** is used at Visit 3 whilst all other visits use the 3 month version.

Abbreviations

CCI	CCI
ADaM	Analysis Data Model
AE	Adverse Event
ANCOVA	Analysis of Covariance
ATC	Anatomical Therapeutic Chemical
BMI	Body Mass Index
CA	Competent Authority
CF	Cystic Fibrosis
CFU	Colony Forming Units
CI	Confidence Interval
CRO	Contract Research Organisation
CS	Clinically Significant
CT	Computerised Tomography
CTP	Clinical Trial Protocol
CTR	Clinical Trial Report
CCI	Data CCI
EC	Ethics Committee
eCRF	electronic Case Report Form
eCOA	electronic Clinical Outcome Assessment
ED	Exposure Day
FEV ₁	Forced Expiratory Volume in one second
FOE	Frequency of Exacerbations
FVC	Forced Vital Capacity
GLI	Global Lung Function Initiative
ICH	International Conference on Harmonisation
IMP	Investigational Medicinal Product
ITT	Intention-To-Treat
IWRS	Interactive Web Response System
MAR	Missing At Random
MedDRA	Medical Dictionary for Regulatory Activities
MI	Multiple Imputation
mITT	Modified Intention-To-Treat (Full Analysis Set)
MIU	Million International Unit
NCFB	Non-CF-Bronchiectasis
NCS	Non Clinically Significant
P. aeruginosa	Pseudomonas aeruginosa
PP	Per-Protocol
PT	Preferred Term
PWP	Prentice, Williams and Peterson
CCI	CCI
CCI	CCI
SAE	Serious Adverse Event
SAP	Statistical Analysis Plan

CONFIDENTIAL

Sponsor:	Zambon S.p.A.	Protocol Number:	Z7224L02
----------	---------------	------------------	----------

SD	Standard Deviation
CCI	CCI
SOC	System Organ Class
SUSAR	Suspected Unexpected Serious Adverse Reaction
TEAE	Treatment Emergent Adverse Event
WHO	World Health Organisation

CONFIDENTIAL

Sponsor:	Zambon S.p.A.	Protocol Number:	Z7224L02
----------	---------------	------------------	----------

1 Introduction

This document presents the Statistical Analysis Plan (SAP) for Zambon, Protocol No. Z7224L02: A double-blind, placebo-controlled, multi-centre, clinical trial to investigate the efficacy and safety of 12 months of therapy with inhaled colistimethate sodium in the treatment of subjects with non-cystic fibrosis bronchiectasis chronically infected with *Pseudomonas aeruginosa* (*P. aeruginosa*)

This analysis plan is based on the final protocol Version 5.0 dated 22Jul2021.

The SAP provides the description of the analysis for the final analyses. Any deviations from the SAP which occur after breaking the blind will be documented and justified in the final clinical trial report (CTR) and deviations will be clearly marked as ‘post hoc’ analysis.

CONFIDENTIAL

Sponsor:	Zambon S.p.A.	Protocol Number:	Z7224L02
----------	---------------	------------------	----------

2 Study Objectives

The primary objective of the trial is to investigate the effect of the use of inhaled colistimethate sodium, administered twice daily via the CCI for 12 months, compared to placebo in subjects with non-cystic fibrosis bronchiectasis (NCFB) chronically infected with *P. aeruginosa* on the annualized frequency of pulmonary exacerbations.

2.1 Primary Endpoint

The primary endpoint of this trial is the mean annual NCFB pulmonary exacerbation rate.

A pulmonary exacerbation is defined as the presence concurrently of at least 3 of the following 8 symptoms/signs for at least 24 hours:

- Increased cough;
- Increased sputum volume and/or consistency;
- Increased sputum purulence;
- New or increased haemoptysis;
- Increased wheezing;
- Increased dyspnoea;
- Increased fatigue/malaise;
- Episodes of fever (temperature $\geq 38^{\circ}\text{C}$);

And it is clinically determined that the subject requires and is prescribed systemic antibiotic therapy.

The start date of a protocol-defined pulmonary exacerbation will be taken as the first day that at least 3 of the pre-defined 8 symptoms/signs occurred concurrently for at least 24 hours, as determined by the Investigator, as documented by the start date of the corresponding AE in the eCRF AE form.

Resolution of a pulmonary exacerbation is defined as the date of completion of the required course(s) of systemic antibiotic treatment and/or the Investigator's judgement that the NCFB pulmonary exacerbation has resolved, as documented by the end date provided for the corresponding AE in the eCRF AE form, whichever is the later of the two dates. The exacerbation end date will be reported at the next scheduled visit or by phone. A new pulmonary exacerbation is only considered to occur if there are at least 14 days between the end of the course of systemic antibiotics and the onset of new qualifying symptoms.

Any episodes of pneumonia during the trial should be considered as pulmonary exacerbations. Episodes of pneumonia which are radiologically confirmed and/or requiring intravenous antibiotics and/or hospitalisation will be considered as severe pulmonary exacerbations. Adverse Events of COVID-19 with symptoms of an exacerbation, requiring antibiotics during the course of the study are considered as pulmonary exacerbations. All pulmonary exacerbations must have the associated

CONFIDENTIAL

Sponsor:	Zambon S.p.A.	Protocol Number:	Z7224L02
----------	---------------	------------------	----------

Pulmonary Exacerbation, Pulmonary Exacerbation Symptoms and Systemic Antibiotic Therapy forms entered into the eCRF, and linked to the corresponding AE.

The treatment of pulmonary exacerbations will follow current treatment regimens used at the respective participating investigational site.

A supportive analysis will be conducted using an alternative definition of NCFB pulmonary exacerbation. The re-classification of exacerbations will be done in a blinded fashion (before database lock). Alternative definition of pulmonary exacerbation: deterioration in three or more of the following key symptoms for at least 48 hours:

- Cough;
- Sputum volume and/or consistency;
- Sputum purulence;
- Breathlessness and/or exercise tolerance (dyspnoea);
- Fatigue and/or malaise;
- Haemoptysis;

And a physician determines a change in bronchiectasis treatment is required when other potential causes of clinical deterioration have been discounted.

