In the case of a partial onset date of NCFB pulmonary exacerbation due to missing day, the onset of the event will be assumed to be the first day of the month. If the resultant derived date is prior to the date of first IMP dose, then it will be assumed to be equal to the first IMP dose date. Resultant derived dates will be reviewed during the blind review meeting and documented in the Blind Data Review and Analysis Sets Report.

In case of a partial resolution date of NCFB pulmonary exacerbation due to missing day, the resolution of the event will be assumed to be the last day of the month. If the resultant derived date is after the treatment completion/discontinuation date, then it will be assumed to be equal to the treatment completion/discontinuation date.

In case a NCFB pulmonary exacerbation presents a symptom with missing duration, following a conservative approach, the longest duration based on the start and stop dates of that symptom and until the resolution date of the NCFB pulmonary exacerbation will be imputed.

Two NCFB pulmonary exacerbations will be considered as a single episode in the statistical analysis if the second exacerbation started less than 14 days after the end of the systemic antibiotic therapy for the previous exacerbation (start date of the exacerbation - end date of the treatment of the previous exacerbation $<$ 14 days). In case of more than two exacerbations for the same subject, this rule will be applied iteratively (therefore, more than two exacerbations may be considered as a single episode). Such cases will be discussed during the blind review of the data and the decisions taken will be documented in the Blind Data Review and Analysis Sets Report.

The above rule will not apply to the analysis of NCFB pulmonary exacerbations as AEs in the safety analysis.

In case of NCFB pulmonary exacerbations considered as a single episode:

CONFIDENTIAL

Sponsor:	Zambon S.p.A.	Protocol Number:	Z7224L02
----------	---------------	------------------	----------

- the start date of the first event will be considered as the start date;
- the stop date of the last event will be considered as the stop date;

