A simple summary of the annualised pulmonary exacerbation rate will be calculated across subjects for each treatment as $\{\sum_i^{n_j} \text{exacerbation}_i / \sum_i^{n_j} \text{exposure}_i\}$ where j denotes randomised treatment group, $i = 1 \dots n_j$ denotes the number of subjects, exacerbation_i and exposure_i denote the number of exacerbations and exposure time for subject i .

The total duration of systemic antibiotic therapy, overall and by route, will be summarised by treatment group using descriptive statistics for continuous variables as well as distribution frequencies for the following categorisations:

- 1-7 days;

CONFIDENTIAL

Sponsor:	Zambon S.p.A.	Protocol Number:	Z7224L02
----------	---------------	------------------	----------

- 8-15 days;
- 16-30 days;
- >30 days;
- Not Evaluable.

The total duration of systemic antibiotic therapy will be summarised overall and by category.

The duration of systemic antibiotic therapy will be evaluated considering the start and end date of the therapy associated with the pulmonary exacerbation. The duration of each course of systemic antibiotic therapy will be calculated using the following formula:

- Duration (days) = stop date – start date +1

For exacerbations treated with more than one systemic treatment, the duration will be calculated by summing the duration of the associated treatments. The overlapping days will be counted only once.

It is expected that all systemic antibiotic therapy will have completed (i.e. will have a stop date) at the end of the study when data are final, as all therapy stop dates are required to be known in order to derive the resolution date of pulmonary exacerbations per the definition described earlier in this section.

In order to calculate the duration of each course of systemic antibiotic therapy, the following rules will be applied for partial dates of start and stop date of systemic antibiotic therapies:

For the start date:

- if only the day is missing, the first day of the month will be assumed. If the resulting derived date is prior to the start date of the exacerbation, then start date of therapy will be assumed to be equal to the start date of the pulmonary exacerbation.
- if the day and the month are missing, then the date will not be imputed and the duration will be classified as “Not Evaluable”.

For the stop date:

- if only the day is missing, the last day of the month will be assumed;

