4.7.6.6 CCI [redacted]

The CCI [redacted] will be presented by treatment group.

The endpoint quantity for each subject will be computed with the following formula:

$$\text{CCI [redacted]} = 365.25 \times \{(\text{follow-up time [days]} - \text{sum of durations of CCI [redacted]}) / \text{follow-up time [days]}\} .$$

Follow-up time will be computed as detailed in Section 4.1.7.

For CCI [redacted] CCI [redacted] [redacted] with a resolution date after the treatment completion/discontinuation, the number of days of duration after the treatment completion/discontinuation, i.e. out of the follow-up period, will be subtracted from the sum of durations of CCI [redacted].

The annualised number of CCI [redacted] days will be compared between the treatment groups using an ANCOVA model including treatment, country, as detailed in Section 4.9.1, and use of stable concomitant therapy with oral macrolides as fixed effects. Least square means in each treatment group, least square mean difference between treatments, their 95% CIs and associated p-value will be estimated. OBSMARGINS option will be used for least square means estimates.

In addition, a summary statistics table will be produced to display:

- For each treatment group:
 - The number of subjects with at least one protocol-defined CCI [redacted], and their:
 - Mean exposure time (months);
 - Total number of CCI [redacted];
 - Mean number of CCI [redacted];
 - Mean duration of CCI [redacted];
 - Total months CCI [redacted].
 - The number of subjects with zero protocol-defined CCI [redacted]s, and their:
 - Mean exposure time (months);
 - Total months CCI [redacted].

CONFIDENTIAL

Sponsor:	Zambon S.p.A.	Protocol Number:	Z7224L02
----------	---------------	------------------	----------

- Overall total months CCI [REDACTED];
- Mean time CCI [REDACTED] (months).
- Difference in mean time CCI [REDACTED] between treatment groups;
- Ratio of mean time CCI [REDACTED] between treatment groups.

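### The rule that separates exacerbations ignores the resolution date, so a separate record opened before the first episode has resolved can count as a second primary event, with its overlapping days subtracted twice

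*SAP*

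**What the plan says.** SAP 2.1 sets the condition for a new event: "only considered to occur if there are at least 14 days between the end of the course of systemic antibiotics and the onset" (that is, of fresh qualifying symptoms). Protocol 9.7 and 10.1.5 use the same interval.

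The same SAP section defines when an exacerbation ends. It takes the completion of antibiotics and the Investigator's judgement of resolution, the latter "as documented by the end date provided for the corresponding AE in the eCRF AE form, whichever is the later of the two dates". Protocol 9.7 makes this the end date of the adverse event and requires weekly calls until it is reached.

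SAP 4.7.4 turns the new-event rule into an algorithm. Two exacerbations are one episode "if the second exacerbation started less than 14 days after the end of the systemic antibiotic therapy for the previous exacerbation". The quantity tested is "start date of the exacerbation - end date of the treatment of the previous exacerbation", compared with 14 days and applied iteratively. The resolution date does not enter.

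SAP 4.7.6.6 (endpoint name redacted, formula partly visible) computes 365.25 × (follow-up days − sum of durations) / follow-up days. Its one stated correction is that days after treatment completion or discontinuation "will be subtracted from the sum of durations of" the events. The sentence "The overlapping days will be counted only once" stands in 4.7.4 and concerns several antibiotic courses within one exacerbation.

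**The concern.** The two definitions use different clocks. An episode may stay open after antibiotics stop, because its end is the later date, while the test for a new episode runs only from the end of antibiotics. The plan can therefore place one patient in two exacerbations on the same day.

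The record pattern needed is specific: a second exacerbation form and linked adverse event, with new qualifying symptoms, starting at least 14 days after the first antibiotic course ended and on or before the end date of the first adverse event.

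Two analyses are exposed. The primary negative binomial model would take two events where the SAP's own resolution rule says the first was still in progress. The days endpoint, which is compared between arms by ANCOVA, would lose the shared days twice.

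**Working it through.** **Inputs from the documents.** Merge threshold: fewer than 14 days from antibiotic end to next start (SAP 4.7.4). Resolution: the later of two dates (SAP 2.1). Days formula: SAP 4.7.6.6. Planning values: placebo rate 1.09 per year, 35% reduction (ratio 0.65), 170 completers per group, power 90%, or 80% for a 30% reduction (Protocol Summary, Sample Size). Randomised: 287 (SAP 3.9), about 143 per arm.

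**Assumptions.** The documents give no frequency of overlapping records; the shares below are illustrative. Dispersion k is redacted. Mean exposure of 0.85 year is assumed. Durations count both end days, since the visible text of 4.7.6.6 gives no duration formula.

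**The plan's own figure.** The point rests on no stated figure. The stated powers serve only to choose k. With power = Φ(√(n / (1/μ0 + 1/μ1 + 2k)) × |ln RR| − 1.96), n = 170 and μ0 = 1.09, k = 0.30 gives 90.7% and 79.0% against the stated 90% and 80%. Values from 0.25 to 0.32 fit both within 2 points.

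**Example 1.** First record: days 1–40, antibiotics to day 14. Second record: days 30–45.
- Merge test: 30 − 14 = 16, not below 14, so 2 events.
- Days subtracted: 40 + 16 = 56.
- Calendar days in any exacerbation: 45. The 11 days from 30 to 40 are taken twice.

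**Example 2, 365 days of follow-up.** First record: days 100–159, antibiotics to day 113. Second record: days 130–159.

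| Handling | Events | Days subtracted | Annualised days |
|---|---|---|---|
| SAP as written (gap 130 − 113 = 17) | 2 | 60 + 30 = 90 | 365.25 × 275/365 = 275.2 |
| Merged on resolution date | 1 | 60 | 365.25 × 305/365 = 305.2 |
| One record with two antibiotic courses, SAP as written | 1 | 60 | 305.2 |

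**Boundary.** With the first adverse event still open to day 159, a second start on day 126 (gap 13) gives 1 event and 60 days. A start on day 127 (gap 14) gives 2 events and 60 + 33 = 93 days for the same 60 calendar days.

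**Effect on the rate ratio.** If shares qP and qA of episodes are counted twice, the observed ratio is 0.65 × (1 + qA)/(1 + qP).

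| qP / qA | Placebo rate | Ratio |
|---|---|---|
| 2% / 2% | 1.11 | 0.650 |
| 10% / 10% | 1.20 | 0.650 |
| 5% / 2% | 1.14 | 0.631 |
| 10% / 5% | 1.20 | 0.620 |
| 2% / 5% | 1.11 | 0.669 |
| 5% / 10% | 1.14 | 0.681 |

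**Effect on power, equal shares.** Mean counts are m0 = 1.09 × 0.85 = 0.927 and m1 = 0.65 × 0.927 = 0.602, or 143 × (0.927 + 0.602) ≈ 219 episodes in all. With k = 0.30, SE = √((1/m0 + 1/m1 + 2k)/143) = 0.1528 and power is 80.5%. Double counting multiplies each 1/m by 1 + q(1 − q)/(1 + q)². At q = 3% (about 7 episodes) the SE is 0.1545 and power 79.6%. At q = 10% (about 22 episodes) the SE is 0.1574 and power 78.1%.

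**Effect on the days endpoint.** Taking 7 to 22 such records with 11 to 30 shared days each, over 286 patients at 0.85 year, the pooled mean falls by roughly 7 × 11/286/0.85 = 0.3 to 22 × 30/286/0.85 = 2.7 days per year.

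**The case against.** A reader might infer that any unresolved episode that is re-treated counts twice. The documents do not support that. SAP 4.7.4 takes the latest end date when several systemic courses are given for one exacerbation, so a further course filed under that exacerbation moves the antibiotic end date and leaves one event. Protocol 10.1.5 describes treatment of a subject not better after the initial course as continuation or escalation, not as a new event. A second event also needs its own forms and, in SAP 2.1, an interval between "the end of the course of systemic antibiotics and the onset of new qualifying symptoms". That part of the objection stands in full. What remains is that the count depends on how the site files the later course, and the algorithm tests dates alone.

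Blinded review is the second defence. The committee in SAP 4.2.1 may ask sites to look again at classification and duration, and 4.7.4 allows start dates to be reviewed against stop dates and antibiotic therapy. This might catch such records. But the Investigator decides, and no written criterion says that a record starting before the previous resolution should be merged.

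Third, the antibiotic anchor is the protocol's consistent definition and rests on a recorded date, whereas resolution may rest on judgement. This stands as a reason not to rewrite the primary definition. So does a practical difficulty: SAP 4.7.4 and 4.11 set a resolution date with a missing day to the end of the month. If antibiotics ended on 3 March and resolution is recorded only as March, resolution becomes 31 March. A new exacerbation on 20 March, 17 days after antibiotics, would then be merged wrongly by an unrestricted resolution-date rule.

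**Conclusion.** The point holds for a narrow record pattern. The merge rule does not use the resolution date, although the SAP defines resolution as "whichever is the later of the two dates". A separate, newly qualifying record that begins 14 or more days after antibiotics and before the first adverse event ends therefore counts as a second primary event. The visible text of 4.7.6.6 has no rule to stop the shared days being subtracted twice; for a single patient the error can be large (30 annualised days in the second example).

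At trial level the effect is probably small. Under the assumed shares, equal occurrence leaves the ratio at 0.65 and costs at most 2.4 points of power (80.5% to 78.1%). A reader might infer a bias in favour of colistimethate sodium, on the argument that slow-resolving episodes are commoner on placebo. The documents give no frequency by arm and no reason for an imbalance in a blinded trial, and the ratio moves as readily to 0.681 as to 0.620. These sizes depend on the assumed shares, dispersion and exposure.

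**What to change.** 1. **SAP 4.7.6.6.** Replace the sum of durations with the number of distinct calendar days in any exacerbation (the union of days), truncated at treatment completion or discontinuation. This needs no new data and leaves the definition of an event unchanged.

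2. **SAP 4.7.4, before unblinding.** Flag every exacerbation record whose start is on or before the resolution date of the previous one, using only resolution dates that are fully recorded. Then either run a sensitivity analysis of the primary rate that merges flagged records into a single episode, applied iteratively as the present rule is, or adopt that merge as the written criterion for the blinded review. Report the number of flagged records, by arm after unblinding.

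The cost is one extra date condition on data already collected. If the merge is adopted, a few event counts fall slightly. Month-end imputed resolution dates must be left out of the condition, so some overlaps with incomplete dates will stay unmerged.
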